## **Germany**

The German Pharmacoepidemiological Research Database (GePaRD) is a population-based database obtained from statutory health insurance agencies (SHIs) in Germany (Jobski et al., 2012; Kraut et al., 2010; Pigeot and Ahrens, 2008). Ninety percent of the population in Germany is insured with the SHIs. The database covers over 15 million SHI members from all regions of Germany, approximately 17% of the German population (population data from Eurostat, 2012). Membership in SHIs is fairly stable over time. The GePaRD includes the following types of data from all patients enrolled in one of the SHIs: demographics, hospital diagnoses, ambulatory care diagnoses and procedures (coded in the International Statistical Classification of Diseases and Related Health Problems, 10th Revision, German Modification [ICD-10-GM]), and ambulatory prescriptions including date of prescription and date of pharmacy dispensing. Although information on dose is not available, the number of boxes prescribed is recorded for each medication.

The German version of the ICD-10-CM is used for coding diagnoses, and OPS (Operationen- und Prozedurenschlüssel) codes are used for surgical and diagnostic procedures. Types of treatments and diagnostic procedures with exact date are registered according to EBM (Einheitlicher Bewertungsmaßstab) codes, developed for payment of physicians for the outpatient treatment of German SHI patients.

Studies are conducted in collaboration with the Bremen Institute for Prevention Research and Social Medicine (BIPS), University of Bremen, Germany; SHI and health ministry approval is needed for the study.

A total of four SHIs contribute data to the GePaRD. Two of these SHIs, involving approximately 4,000 users of cilostazol, approved participation in the study. Data from a third SHI, which also approved participation and included 44 users of cilostazol, are considered inadequate as follow-up is truncated at the end of 2007. These data will not be included in the study. The fourth SHI denied participation in the study. This SHI denied approval because the study protocol did not include an evaluation of current treatment recommendations from the Federal Joint Committee (G-BA) concerning

cilostazol. Submission of a revised protocol that included additional analyses to evaluate these recommendations was unsuccessful.

## **United Kingdom**

In the UK, nearly all residents are registered in a general medical practice that uses electronic medical records. Based on those records, there are two main databases available for research purposes: the Clinical Practice Research Datalink (CPRD), formerly the General Practice Research Database (GPRD), and the The Health Improvement Network (THIN). Both databases have similar information recorded by general practitioners (GPs). Furthermore, there is an overlap of GP practices and patients between CPRD and THIN of approximately 30%. The CPRD database is available through the UK Medicines and Health Care Products Regulatory Agency (MHRA). The THIN database is available through Cegedim Strategic Data.

Established in 2002, THIN now collects data from more than 400 practices, covering 5% of the general population, with more than 57 million patient-years of experience (Cegedim Strategic Data Medical Research UK, 2012). Ten million individual patients are represented in the data; of those, approximately one-third are active at any one time. THIN records information on all services provided by the general practitioner.

All practices record information received on hospital admissions, discharge diagnoses, and medications; outpatient specialist visits; and outcomes of treatment. For some of the practices, THIN offers additional hospital episode data linked to the general practice patients. When a drug is prescribed, a computer record is immediately created and added to the database. The THIN database has been validated as accurately recording a patient's health care (Denburg et al., 2011), and pharmacoepidemiologic studies using THIN data have been published in scientific journals (e.g., Choi et al., 2012; Hayes et al., 2011).

THIN supplies de-identified data for approved drug safety and epidemiological studies. Such research needs to be approved by the South East Multicentre Research Ethics Committee ([http://www.thin-uk.com/contributing\\_data.htm](http://www.thin-uk.com/contributing_data.htm)).

## **Sweden**

In Sweden, the national health care system provides universal coverage to all residents (9.4 million inhabitants). Health care coverage includes visits to general practitioners (GPs), specialists, hospital admissions, and hospital outpatient visits; drug costs are either partially or completely covered. A centralised civil registration system has been in place for many years, allowing for personal identification of each person in the entire population and for the possibility of linkage to all national registers containing civil registration numbers, e.g., patient register, cancer register, prescription databases, register of causes of death, and population registers (Furu et al., 2010). The National Inpatient Register covers all publicly run in-patient care in Sweden from 1987 and includes information on diagnoses, surgical procedures, and in-hospital deaths. Since 2001, the government has empowered the National Board to collect information on outpatient hospital care as well. The register includes about 1.5 million discharges annually. Since 1997, diagnoses have been coded using ICD-10 codes. Whereas coverage of the

---

 Population data from Eurostat. 2011. Available at: <http://epp.eurostat.ec.europa.eu/portal/page/portal/population/data/database>. Accessed 22 August 2012.

inpatient register is currently almost 100%, coverage of hospital-based outpatient care is considerably lower (about 80%) (Ludvigsson et al., 2011). Visits to GPs and specialists outside the hospitals are not included in the registers. Data collected in these registers can be made available for research purposes under the principles for protection and release of sensitive data (Ludvigsson et al., 2011; Ministry of Justice, 2009; 2012).

The Swedish National Prescription Database provides patient-level data on all dispensed and prescribed drugs (reimbursed and nonreimbursed) in ambulatory care to the whole population of Sweden since July 2005. The following data on drugs are available: drug substance, brand name, formulation and package, dispensed amount, dosage, expenditure and reimbursement, date of prescribing and dispensing, place of residence of the patient, practice issuing the prescription, and prescriber's specialty (Wettermark et al., 2007).

Data requests for research purposes require collaboration with university or affiliated researchers and ethics committee approval.

**Table 9. Main Features of Selected European Databases**

	Database and Size of Population Size of the Country				
Feature	IACS, Aragón, Spain (N = 1,346,293)a	SIDIAP, Catalonia, Spain (N = 7,565,603)b	German Pharmacoepidemiological Research Database (GePaRD) (N = 81,751,602)c	THIN, United Kingdom (N = 62,435,709)c	Swedish Prescription and Inpatient National Databases (N = 9,415,570)c
Database type	Primary health care electronic medical record database; link to hospital discharge and pharmacy data	Primary health care electronic medical record database; link to hospital discharge, pharmacy, and mortality data	Claims databases, 4 Statutory Health Insurance (SHI) plans d	Primary health care electronic medical record database	National health record databases capable of linkage though the unique civil personal registration number
Database population	1.3 million	5.8 million (1.9 million in up-to-standard practices)	14 million (fewer patients might be included in research projects)	3.4million	9.4 million
Proportion of the country's population covered by the database	2.8%	12.2% (4.0%; refers to the 1.9 million in up-to-standard practices)	17%	5%	100%
Representativeness of patients	Total population covered	Pending	Representative of sex and age of German population	Representative of sex and age of UK population	Total population covered
Data on medications	Reimbursed pharmacy-dispensed prescriptions	All drugs prescribed in primary health centres; all reimbursed drugs dispensed by community pharmacies	Reimbursed pharmacy-dispensed prescriptions	All prescriptions by GPs	All pharmacy-dispensed prescriptions
Dose	Formulation strength	Prescribed dose	Formulation strength	Prescribed dose	Formulation strength

Database and Size of Population Size of the Country					
Feature	IACS, Aragón, Spain (N = 1,346,293)a	SIDIAP, Catalonia, Spain (N = 7,565,603)b	German Pharmacoepidemiological Research Database (GePaRD) (N = 81,751,602)c	THIN, United Kingdom (N = 62,435,709)c	Swedish Prescription and Inpatient National Databases (N = 9,415,570)c
Duration	Based on prescriptions	Based on prescriptions	Based on prescriptions	As indicated in the prescription	Based on prescriptions
Drug dictionary codes/ therapeutic classification	ATC	ATC	ATC	Multilex/British National Formulary	ATC
Clinical indication	Not specifically recorded but based on proxies	Not specifically recorded but based on proxies	Not specifically recorded but based on proxies	Associated with new courses of medications, but completeness is variable Computerised free-text information is available for review	Not specifically recorded but based on proxies
Primary care diagnosis	Yes	Yes	Yes Since January 2004	Yes	No. Diagnoses from outpatient hospital clinics are available
Hospital diagnosis	Yes	Yes (CMBD-AH)	Yes	Recorded by GPs	Yes
Recorded by primary care physicians	No	No	No	Yes	No
Available from hospital database or hospital claims	Yes CMBD-AH	Yes CMBD-AH	Yes	Partial linkage to HES	Yes

Database and Size of Population Size of the Country					
Feature	IACS, Aragón, Spain (N = 1,346,293) a	SIDIAP, Catalonia, Spain (N = 7,565,603) b	German Pharmacoepidemiological Research Database (GePaRD) (N = 81,751,602) c	THIN, United Kingdom (N = 62,435,709) c	Swedish Prescription and Inpatient National Databases (N = 9,415,570) c
Disease and procedure codes	Primary health care: ICPC Hospital: ICD-9	ICD-10-CM	ICD-10-GM	Read codes	ICD-10-CM
Lifestyle risk factors	No	Yes	No	Yes	No
Data availability	Partial since 2005; Complete since 2010	Since 2006	Since 2004	Since 1980	Since July 2005
Approximate time lag (updates)	1 year	1 year	1.5 years	6 months	2012 data will be available in 3-4Q 2013
Approval process for database research	Data application and ethics committee approval required	Data application and ethics committee approval required	Approvals by SHI and Health Ministry are required	Ethics or scientific approval is required	Data application and ethics committee approval required

ATC = Anatomical Therapeutic Chemical; CMBD-AH = Catalan Health Services database of hospital admissions; GP = general practitioner; HES = Hospital Episode Statistics; IACS = Aragón Health Sciences Institute ; ICD-10 = International Statistical Classification of Diseases and Related Health Problems, 10th Revision; ICD-10-CM = International Statistical Classification of Diseases and Related Health Problems, 10th Revision, Clinical Modification; ICD-10-GM = International Statistical Classification of Diseases and Related Health Problems, 10th Revision, German Modification; ICPC = International Classification of Primary Care (codes); SHI = Statuary Health Insurance (Germany); SIDIAP = Information System for the Advancement of Research in Primary Care; THIN= The Health Improvement Network Database; UK = United Kingdom.

a Gobierno de Aragón [Government of Aragón]. Available at:

[http://www.aragon.es/DepartamentosOrganismosPublicos/Organismos/InstitutoAragonesEstadistica/AreasTematicas/Demografia/CifrasPoblacion/ci.02\\_Cifras\\_oficiales\\_poblacion.detalleDepartamento?channelSelected=448c2135fc5fa210VgnVCM100000450a15acRCD](http://www.aragon.es/DepartamentosOrganismosPublicos/Organismos/InstitutoAragonesEstadistica/AreasTematicas/Demografia/CifrasPoblacion/ci.02_Cifras_oficiales_poblacion.detalleDepartamento?channelSelected=448c2135fc5fa210VgnVCM100000450a15acRCD). Accessed 19 November 2012.

b Generalitat de Catalunya. Available at: <http://www.gencat.cat/catalunya/eng/coneixer-poblacio.htm>. Accessed 19 November 2012.

c Population data from Eurostat. 2011. Available at: <http://epp.eurostat.ec.europa.eu/portal/page/portal/population/data/database>. Accessed 22 August 2012.

d Two SHIs agreed to contribute data to the study, providing approximately 4,000 users of cilostazol. One SHI denied approval for participation, and data from a second SHI involving 44 users of cilostazol are truncated to the end of 2007 and are considered inadequate.

## 9.5 Study Size

The study size is driven by the uptake of cilostazol in the populations from which the automated databases obtain data. For each database, we will identify all new users of cilostazol since the drug became available in the country.

We ascertained the preliminary number of users of cilostazol in SIDIAP, THIN, and Swedish databases (Table 10). For the GePaRD, we estimated the number of users of cilostazol in the database based on the sales data in Germany provided by Otsuka. For IACS in Spain, the number of users is yet to be ascertained. Overall, the estimated total number of users in the study databases is approximately between 11,000 and 17,000 (pending number of users from IACS and confirmation from the GePaRD and Sweden). This estimation does take into account the study exclusion criterion of 6 months of continuous enrolment in the database.

**Table 10. Preliminary Number of Users of Cilostazol in the Study Databases**

Database	Preliminary Number of Users	Comment
IACS, Spain	Pending	
SIDIAP, Spain	3,375	Identified in the database
GePaRD, Germany	4,867 to 9,735	Estimated from sales data in Germany
THIN, UK	1,640	Identified in the database
Sweden (users by year)		Identified in the Swedish National Pharmacy Register a
2008	441	
2009	934	
2010	1,170	
2011	1,067	
2008-2011	1,800 to 2,200	Estimated minimum and maximum number of unique users for the period 2008-2011

a National Board of Health and Welfare. Statistics database. Available at: <http://www.socialstyrelsen.se/statistik/statistikdatabas> and Drug statistics. Available at: <http://192.137.163.49/sdb/lak/val.aspx>. Accessed November 2012.

In Table 11 we present the level of precision in different scenarios of available number of users of cilostazol for different prevalence of diseases and conditions including off-label use. In general, the 95% level of confidence is adequate for prevalences as low as 1% and 1,500 users of cilostazol.

**Table 11. Binomial Confidence Intervals for Different Study Sizes and Prevalence of Disease and Conditions Including Off-Label Use**

Number of Patients	Lower and Upper Bounds of 95% Confidence Intervals for Various Prevalences of Diseases (%)									
	1%		2%		5%		7%		10%	
1,500	0.6	1.6	1.4	2.8	4.0	6.2	5.8	8.4	8.6	11.6
2,000	0.6	1.5	1.4	2.7	4.1	6.0	5.9	8.2	8.7	11.4
4,000	0.7	1.4	1.6	2.5	4.3	5.7	6.2	7.8	9.1	11.0
6,000	0.8	1.3	1.7	2.4	4.5	5.6	6.4	7.7	9.3	10.8
8,000	0.8	1.2	1.7	2.3	4.5	5.5	6.5	7.6	9.4	10.7

Note: Calculated with Episheet (Rothman, 2011).

## 9.6 Data Collection and Management

Routine procedures will include checking electronic files, maintaining security and data confidentiality, following analysis plans, and performing quality-control checks of all programs. Each database custodian will maintain any patient-identifying information securely on site according to internal standard operating procedures.

Security processes will be in place to ensure the safety of all systems and data. Every effort will be made to ensure that data are kept secure so that they cannot be accessed by anyone except select study staff.

Appropriate data storage and archiving procedures will be followed (i.e., storage on CD-ROM or DVD), with periodic backup of files to tape. Standard procedures will be in place at each research centre to restore files in the event of a hardware or software failure.

## 9.7 Data Analysis

The use of cilostazol will be ascertained by the following analysis. Draft shells of the analysis tables are provided in separate Excel files (DUS1: Cilostazol shell analysis tables Final.xlsx; DUS2: Cilostazol shell analysis tables DUS2.xlsx ).

### 9.7.1 Number of Users and Patterns of Use

Analysis Tables 1, 2, and 29: Use of cilostazol during the study period. Number of users; number of prescriptions; number of packages; total number of DDDs; mean number and standard deviation (SD) of packages and DDDs per prescription; and mean (SD) number of prescriptions, packages, and DDDs per user. Analyses will be stratified by year of start of cilostazol (DUS1 only) and formulation: 50 mg and 100 mg (Analysis Table 1), and by formulation and package size (Analysis Table 2). The number and percentage of users by the number of prescriptions received during follow-up will be calculated (Analysis Table 29). The number of users of cilostazol with less than 12 months of continuous enrolment in the database will also be ascertained (Analysis Table 1A).

Analysis Tables 3 and 30: Distribution of users at the start date. Number of users, number of prescriptions, number of packages, number of DDDs, mean (SD) number of packages per user, and mean (SD) number of DDDs per user will be ascertained at the start date for each combination of formulation and package size. The distribution of users by year of start date will be generated (DUS1 only) (Analysis Table 30).

Analysis Tables 4, 25, and 31: Age and sex distribution of users at the start date. The number and percentage of users at the start date will be described by sex and the following groups of age (in years): (1) < 18, 18-29, 30-39, 40-49, 50-59, 60-69, 70-79, ≥ 80 and (2) < 70 and ≥ 70 (Analysis Table 4). Age- and sex-specific prevalence of users of cilostazol during the study period will be calculated (Analysis Table 25). For DUS2, prevalence of use will be calculated as the proportion of patients from the source population who received at least one prescription for cilostazol during 2014 (includes new users and prevalent users). In addition, the mean (SD) of age by sex among cilostazol users at first use will be calculated (Analysis Table 31).

Analysis Table 5: Daily dose at the start date. Daily dose prescribed at the start date will be calculated using the recorded information on strength and quantity prescribed and the days of supply of the first prescription for cilostazol. The daily dose prescribed at the start date will be described by sex and age group (< 70 years, ≥ 70 years).

Analysis Table 6: Person-years of use. Person-years of use will be accumulated for each user of cilostazol and across all users. Person-years of use will be described by sex and age (< 70 years, ≥ 70 years). The mean (SD), median, 25th percentile, and 75th percentile (P75) of person-years will be calculated by sex and age group (< 70 years, ≥ 70 years).

Analysis Table 7: Duration of continuous use. Duration of use refers to the duration of continuous treatment with cilostazol. Duration will be ascertained by the total number of days of supply of consecutive prescriptions, defined as those prescribed with a maximum interval of 60 days between dates of consecutive prescriptions. Sensitivity analyses will be conducted for a maximum interval of 90 days between dates of consecutive prescriptions. Person-years of consecutive use will be accumulated for each user of cilostazol and across all users. Person-years of consecutive use will be described by sex and age group (< 70 years, ≥ 70 years). The mean (SD), median, 25th percentile, and 75th percentile of person-years of consecutive use will be calculated by sex and age group (< 70 years, ≥ 70 years).

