**Figure 1. Overview of Study Design**

## 9.2 Setting

### 9.2.1 Source Population

The source population includes all individuals registered in the study databases since the date of the first recorded prescription of cilostazol in each database.

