### 9.2.2 Study Period

The study period is defined in each database as the time between the date when cilostazol became available in the corresponding country and the latest date of data availability (Table 2). The estimated end of study period for IACS, GePaRD, and Sweden will be 31 December 2011. Partial data for the year 2012 are expected to be available in SIDIAP and THIN.

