**Table 2. Estimated Study Period in Each Study Database**

	IACS, Spain	SIDIAP, Spain	GePaRD, Germany	THIN, UK	National Databases, Sweden
Cilostazol launch in country a	Jun 2009	Jun 2009	Jan 2007	Jun 2002	Apr 2008
Study period (based on cilostazol launch date and data availability, end of 2012 or early 2013)	Jan 2010 – Dec 2011	Jun 2009 – Apr 2012	Jan 2007 – Dec 2011	Jun 2002 – Dec 2012	Apr 2008 – Dec 2011

[figure not shown]
GePaRD = German Pharmacoepidemiological Research Database; IACS = Aragón Health Sciences Institute; SIDIAP = Information System for the Advancement of Research in Primary Care database, Catalonia, Spain; THIN = The Health Improvement Network, United Kingdom; UK = United Kingdom.

a Provided by Otsuka.

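### Analysis Table 25 sets a multi-year DUS1 prevalence beside a one-year DUS2 prevalence, so the two figures are not comparable

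*Protocol*

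**What the plan says.** Section 9.7.1 of the Protocol plans, for Analysis Table 25: "Age- and sex-specific prevalence of users of cilostazol during the study period will be calculated (Analysis Table 25". Section 9.2.2 defines the study period as "the time between the date when cilostazol became available in the corresponding country and the latest date of data availability". Table 2 gives the resulting DUS1 windows; the longest is THIN, "Jun 2002 – Dec 2012", and the shortest is IACS, January 2010 to December 2011.

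The next sentence of Section 9.7.1 gives DUS2 its own definition, the "proportion of patients from the source population who received at least one prescription for cilostazol during 2014", counting new and prevalent users together.

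The denominator is the source population, which Section 9.2.1 defines as "all individuals registered in the study databases since the date of the first recorded prescription of cilostazol in each database". The Abstract is likewise cumulative, starting from the date of cilostazol availability. Section 9.2.2.1 sets a new study period for DUS2, but no section sets a new source population.

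Section 8 makes DUS1 the baseline and gives DUS2 the task of evaluating the effect of the measures on prescribing. Section 9.3.6 says that DUS2 results will be compared with those of DUS1. The Abstract and Section 7 say that DUS2 follows the same protocol as DUS1.

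**The concern.** Two different quantities carry one name in one table. Over a common denominator, the number of distinct people who used a drug at some time in several years cannot be smaller than the number who used it in any one of those years. A DUS1 figure built on several years will therefore tend to exceed a one-year DUS2 figure even when prescribing has not moved.

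The measures aim at a more restricted target population (Section 9.3.6), so a lower prevalence in 2014 is what a reader would expect from success. An unexplained fall in Table 25 could be credited to the SmPC changes when part or all of it comes from the shorter window. A true rise in use could equally be hidden.

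The denominator adds a smaller problem. Read literally, people who died or left a database before 2014 still count in the 2014 denominator, although they could not receive a prescription in that year.

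**Working it through.** The Protocol states no prevalence figure to reproduce. The check uses the Swedish counts in Table 10, the only database with both yearly users and users over the whole window.

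**Inputs**
- Swedish users by year (Table 10): 441 (2008), 934 (2009), 1,170 (2010), 1,067 (2011).
- Swedish users over 2008-2011 (Table 10): 1,800 to 2,200, described as "Estimated minimum and maximum number of unique users for the period 2008-2011".
- Swedish population (Table 9): 9,415,570.
- DUS1 windows (Table 2): IACS 24 months, SIDIAP 35, Sweden 45, GePaRD 60, THIN 127 (about 10.6 years).

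**Consistency of the Swedish estimate.** Unique users must lie between the largest single year, 1,170, and the sum of the years, 441 + 934 + 1,170 + 1,067 = 3,612. The range 1,800 to 2,200 does.

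**Effect of the window alone (Sweden, fixed denominator)**
- DUS1-style prevalence: 1,800/9,415,570 = 19.1 and 2,200/9,415,570 = 23.4 per 100,000.
- One-year prevalence in 2011: 1,067/9,415,570 = 11.3 per 100,000.
- If 2014 equalled 2011: 1,067/1,800 = 0.593 and 1,067/2,200 = 0.485, an apparent fall of 41% to 52%.
- If 2014 equalled the peak year 2010: 1,170/1,800 = 0.650 and 1,170/2,200 = 0.532, a fall of 35% to 47%.

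Comparing 2011 with 2014, each over the people registered in that year, removes this artefact.

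**Illustration for the other databases (assumptions, not document figures).** Suppose use is constant. Let T be the DUS1 window in years, T2 the years from the start of that window to the end of 2014, m the calendar years of use per user, and r the yearly population turnover, taken as 0 to 10%. Then

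DUS2/DUS1 = (m/T) × (1 + rT)/(1 + rT2).

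Sweden gives m = 3,612/2,200 = 1.64 to 3,612/1,800 = 2.01. These values are carried to every database and capped at T. The first factor is the window effect. The second is the part of the cumulative denominator that differs between the studies.

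| Database | T | T2 | m/T | Second factor at r = 10% | DUS2/DUS1, r = 0 to 10% |
|---|---|---|---|---|---|
| IACS | 2.0 | 5.0 | 0.82-1.00 | 1.20/1.50 = 0.80 | 0.66-1.00 |
| SIDIAP | 2.9 | 5.6 | 0.56-0.69 | 1.29/1.56 = 0.83 | 0.47-0.69 |
| Sweden | 3.75 | 6.75 | 0.44-0.54 | 1.375/1.675 = 0.82 | 0.36-0.54 |
| GePaRD | 5.0 | 8.0 | 0.33-0.40 | 1.50/1.80 = 0.83 | 0.27-0.40 |
| THIN | 10.6 | 12.6 | 0.16-0.19 | 2.06/2.26 = 0.91 | 0.14-0.19 |

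The order of the databases is more reliable than the sizes. The Swedish m comes from four calendar years. It is probably too low for a window above 10 years, which exaggerates the THIN effect, and too high for a 2-year window, which understates the IACS effect.

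If only DUS2 used people registered in 2014, so that the second factor becomes 1 + rT, the ratios would be 0.16-0.39 in THIN and 0.82-1.20 in IACS. The window effect therefore remains in the long-window databases whatever the 2014 denominator.

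**The case against.** The strongest reply is that prevalence is not a planned impact measure. Table 7 and the list after it in Section 9.3.6 name smoking, visits, discontinuation, contraindications, concurrent platelet aggregation inhibitors and daily dose. Prevalence is absent there and from the Section 8 objectives, and the amendment log (Table 1) calls Table 25 an additional analysis. This stands: a reader might infer that prevalence is a formal test of the measures, and the Protocol does not say so. It does not make the two figures comparable, and the general statements in Sections 8 and 9.3.6 invite the comparison.

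Three other strong readings are tempting and are not supported.

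- *A fall is certain in every database.* The only documented size is Swedish, and its whole-period count is a pre-study estimate. The effect may be small or nil in IACS.
- *The THIN denominator is about three times too large.* Section 9.4.2 says that of ten million patients represented, "approximately one-third are active at any one time". Table 9 dates THIN data from 1980, whereas Section 9.2.1 counts people registered since the first recorded cilostazol prescription, and launch was in June 2002. People who left before then are outside the denominator. The cumulative definition also dilutes DUS1, so a total dilution is not the bias between the studies.
- *The pooled DUS1 baseline for Analysis Tables 17, 18, 20 and 28 is invalid and needs a different main comparator.* Those tables do pool start years, but the Protocol gives no figure for change over calendar time, and the choice of comparator is debatable.

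Two possible repairs fail. Analysis Tables 1 and 30 split DUS1 by year of start, which describes new users and not everyone using the drug in a year. Counting prevalent users in DUS2 does not close the gap either, because DUS1 begins at or near launch and so already captures nearly all users.

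**Conclusion.** The point holds for Analysis Table 25. The Protocol itself fixes both definitions, and they measure different things, so this is not a detail left to a later analysis plan. On the Swedish counts, unchanged use would appear as a fall of about 41% to 52%, or 35% to 47% against the 2010 level. This rests on the Table 10 estimate of unique users, on a common denominator, and on 2014 use equal to 2011 or 2010. The effect should grow with the length of the DUS1 window.

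The denominator is a secondary point. As written it includes people no longer registered in 2014, but DUS1 shares the fault. Only the added years differ, worth a factor of 0.80 to 0.91 at an assumed turnover of 10% a year and nothing at zero turnover. The finding is confined to Table 25 and should be corrected before the two prevalences are reported together.

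**What to change.** In Analysis Table 25:

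1. Add one-year DUS1 prevalence by calendar year, or at least for the last full DUS1 year, on the DUS2 definition (new plus prevalent users in that year). By Table 2 the last full year is 2011 in IACS, SIDIAP, GePaRD and Sweden. For THIN it is 2012 if that year is complete; Section 9.2.2 expected only partial 2012 data, so otherwise it is 2011.
2. In both studies, use as denominator the people registered in that year, or the mid-year population, and state this in Section 9.7.1.
3. Compare 2014 with the last full DUS1 year.
4. If whole-period DUS1 prevalence is kept, state beside it that it is not comparable with the 2014 figure.

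The cost is some re-tabulation of existing DUS1 data with yearly denominators. Section 6.1 reports DUS1 complete in four databases by January 2015, with the final report planned for April 2015, so up to five centres would have to return to finished work. No new data collection is needed. If re-tabulation is not possible, the statement in item 4 is the minimum.

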## 8 Research Question and Objectives

The primary objectives of the DUS are as follows:

- To describe the characteristics of new users of cilostazol according to the following factors:
  - Demographics (e.g., age and sex)
  - Baseline comorbidity including conditions listed in the SmPC and the risk management plan (RMP) as potential or identified safety concerns (Otsuka Pharmaceutical Europe Ltd, 2012).
  - Baseline and concurrent use of medications potentially interacting with cilostazol and other medications

- Specific comorbidity and use of medications considered in the proposed risk minimisation measures, specifically those included in the proposed changes to the SmPC
- To describe the duration of the use of cilostazol and discontinuation patterns

Secondary objectives of the DUS are as follows:

- To quantify and describe off-label prescribing
- To describe dosage patterns of the use of cilostazol
- To assess the proportion of patients who are hospitalised for any cause while treated with cilostazol
- To describe the medical specialties of physicians prescribing cilostazol

The study objectives are the same for DUS1 and DUS2. DUS1 provides the baseline characteristics of users of cilostazol before the implementation of SmPC changes and communication with HCPs. DUS2 will be conducted after the implementation of these measures to evaluate their impact on the prescribing of cilostazol.

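### Prevalence of use in Analysis Table 25 spans the whole study period in DUS1 (2.0 to 10.6 years) but only 2014 in DUS2, so the two rounds are not comparable

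*Protocol*

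**What the plan says.** Section 9.7.1 gives the general rule for Table 25: "Age- and sex-specific prevalence of users of cilostazol during the study period will be calculated (Analysis Table 25"). Section 9.2.2 sets the length of that period for DUS1: "The study period is defined in each database as the time between the date when cilostazol became available in the corresponding country" and the last available data. Table 2 turns this into dates for each database, for example "Jan 2010 – Dec 2011" for IACS and "Jun 2009 – Apr 2012" for SIDIAP.

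For DUS2, section 9.7.1 adds a separate rule: "prevalence of use will be calculated as the proportion of patients from the source population who received at least one prescription for cilostazol during 2014". It counts continuing as well as new users.

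Section 8 says DUS2 is carried out after the label changes to "evaluate their impact on the prescribing of cilostazol". Section 9.3.6 says its results will be set against those of DUS1. The protocol specifies no annual prevalence for DUS1 and no common window for the two rounds.

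**The concern.** The proportion of a population that has ever used a drug grows with the length of the window, because each further year adds people who started and stopped. A multi-year figure and a one-year figure therefore differ even if prescribing has not changed. Here both carry the same name and table number, and the shorter window falls after the 2013 label changes.

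With the same denominator, the artefact always points towards lower use in DUS2. A reader could take it for an effect of the risk minimisation measures. The DUS1 figures have the same problem among themselves, since a 2-year window in one database would sit beside a 10.6-year window in another.

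**Working it through.** **1. Window lengths (Table 2; section 9.2.2.1 for DUS2)**

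| Database | DUS1 window | Months | Years | DUS2 |
|---|---|---|---|---|
| IACS | Jan 2010 to Dec 2011 | 24 | 2.0 | 12 months |
| SIDIAP | Jun 2009 to Apr 2012 | 35 | 2.9 | 12 months |
| Sweden | Apr 2008 to Dec 2011 | 45 | 3.75 | 12 months |
| GePaRD | Jan 2007 to Dec 2011 | 60 | 5.0 | 12 months |
| THIN | Jun 2002 to Dec 2012 | 127 | 10.6 | 12 months |

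**2. The protocol's own figure.** Sweden is the only database with both yearly and whole-period counts. Table 10 gives 441, 934, 1,170 and 1,067 users in 2008 to 2011, and a range of 1,800 to 2,200 described as "Estimated minimum and maximum number of unique users for the period 2008-2011". The range cannot be derived from the yearly counts. It does lie within their logical limits: at least the largest year (1,170) and at most the sum (441 + 934 + 1,170 + 1,067 = 3,612).

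**3. Apparent fall in Sweden if use is unchanged.** Formula: 1 − (users in one year ÷ unique users in the whole period), with the same denominator in both rounds.

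| Reference year | against 1,800 | against 2,200 |
|---|---|---|
| 2010 | 1 − 1,170/1,800 = 35.0% | 1 − 1,170/2,200 = 46.8% |
| 2011 | 1 − 1,067/1,800 = 40.7% | 1 − 1,067/2,200 = 51.5% |

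Per 100,000 of the 9,415,570 inhabitants in Table 9, the whole-period figure is 19.1 (1,800) to 23.4 (2,200). The one-year figure is 11.3 (2011) or 12.4 (2010).

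**4. Other databases: illustration only.** No yearly counts are given. Assume constant initiation since launch, exponential time on treatment with mean D, and the same denominator in both rounds. For a window of T years starting at launch, apparent fall = 1 − [1 + D(1 − e^(−(T−1)/D))]/T. For IACS, whose window opens 7 months after launch (L = 7/12), T − 1 becomes T + L − 1 and the divisor becomes T + D(1 − e^(−L/D)).

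| Database | D = 2.0 years | D = 0.5 years |
|---|---|---|
| IACS | 16% | 37% |
| SIDIAP | 23% | 49% |
| Sweden | 33% | 60% |
| GePaRD | 45% | 70% |
| THIN | 72% | 86% |

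**5. Sensitivity to the denominator.** Section 9.2.1 defines the source population as everyone registered since the first recorded cilostazol prescription, so a literal DUS1 denominator also grows where registration turns over. Section 9.4.2 says about one-third of THIN's ten million patients are active at any one time. If the DUS1 denominator were three times the 2014 one (an upper bound), the THIN range would shrink to between 1 − 3 × 0.28 = 16% and 1 − 3 × 0.14 = 58%.

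**The case against.** **Scope.** A reader might infer that prevalence would appear to fall by a third to a half in every database. The documents do not support that. The figure rests on one 3.75-year window and on a whole-period count that is itself an estimate without a derivation. Swedish use was also still building up after the April 2008 launch. Nor is it established that the artefact is larger in THIN than in IACS, because the denominator may offset it.

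**Role of the measure.** No objective in section 8 names prevalence. The comparison in section 9.3.6 leads to Table 7, which lists smoking, visits, discontinuation, contraindications, antiplatelet use and dose. The amendment table records Table 25 as an additional analysis from version 2.1. It would therefore be wrong to say that a specified impact measure is broken. What stands is that the protocol compares the two rounds in general terms, with no caveat excluding Table 25.

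**Disclosure.** The DUS2 rule is explicit, the DUS1 windows are tabulated, and the table shells are in separate files that are not shown. A yearly DUS1 breakdown might exist there. But the protocol text itself fixes both definitions, and they differ. The yearly results it does describe (Tables 1 and 30) go by year of starting cilostazol, so they do not count everyone using it in a year.

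**Age.** A reader might also infer that the DUS1 age-specific figure has no meaning. That goes too far. Table 25 is described under age and sex at the start date, which suggests that numerator age is age at first prescription. What remains open is mainly the age basis of the denominator.

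**Conclusion.** The point holds as a defect of comparability. Read as written, Table 25 reports cumulative use over 2.0 to 10.6 years in DUS1 and 12-month prevalence in DUS2 under one name.

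In Sweden the resulting apparent fall is about 35-52%. This assumes that 2014 use equals the 2010 or 2011 count, that the Table 10 range of unique users is right, and that both rounds use the same denominator. Elsewhere the size cannot be determined from the protocol. It depends on window length, on how long patients stay on treatment, and on whether the DUS1 denominator accumulates with registration turnover. The percentages in step 4 of the working are illustrations under stated assumptions, not estimates.

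The change should be made, but the objectives and the Table 7 measures do not depend on it.

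**What to change.** In section 9.7.1, define Table 25 in both rounds as calendar-year prevalence: persons with at least one prescription in the year, divided by the population registered in that year, by sex and by age in that year. Report it for at least the last full DUS1 year and for 2014. By Table 2, 2011 lies wholly inside all five DUS1 windows and could serve as a common reference year. If the whole-period DUS1 figure is kept, label it 'cumulative use' and state that it is not to be compared with DUS2.

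No new data source or patients are needed, but the cost is more than a change of wording. Section 6.1 reports DUS1 complete in THIN, IACS, SIDIAP and Sweden by 30 January 2015. The change therefore means a modest re-count of existing DUS1 data, plus yearly population denominators by age and sex, at each data custodian. The Swedish yearly counts in Table 10 are shown without age or sex, so they would not be enough.
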